8.1.3.2 Objective Response Rate

The proportion of subjects with a complete remission (CR), complete remission with incomplete bone marrow recovery (CRi) or partial remission (PR) based on the NCI-WG criteria in Section 5.3.3.1 will be estimated and the corresponding 95% confidence interval for the proportion will be constructed. The exact binomial distribution will be used to construct this confidence interval.

A subject will be classified as a complete remission (CR), complete remission with incomplete bone marrow recovery (CRi), partial remission (PR) or as having PD based on the definition in Section 5.3.3.1. The objective response rate (CR, CRi, PR) will be computed for all subjects with active disease at baseline (in the opinion of the investigator).

8.1.3.3 Time to Tumor Progression

Time to tumor progression for a given subject will be defined as the number of days from the date the subject started study drug to the date of the subject's tumor progression. Time to tumor progression may be collected up to 2 cycles (42 days) following the date of the last available tumor evaluation. All events of tumor progression will be included,

regardless of whether the event occurred while the subject was still taking study drug, or after the subject discontinued study drug. If a subject has not progressed, then the data will be censored at the date of the last study visit at which a tumor assessment was performed.

The distribution of the time to tumor progression will be estimated using Kaplan-Meier methodology. Median time to tumor progression and the corresponding 95% confidence interval will be estimated.

8.1.3.4 Overall Survival

Time to death for a given subject will be defined as the number of days from the date the subject started study drug to the date of the subject's death. All events of death will be included, regardless of whether the event occurred while the subject was still taking study drug, or after the subject discontinued study drug. If a subject has not died, then the data will be censored at the date of the last study visit, the last contact date, or the date the subject was last known to be alive, whichever is last. The date of the last study visit will be determined by selecting the last available date of the following study procedures for a subject: physical examination, vital signs assessment, blood chemistry, hematology, and urinalysis collection.

The distribution of the time to death will be estimated using Kaplan-Meier methodology. Median survival time and the corresponding 95% confidence interval will be estimated.

8.1.3.5 Duration of Overall Response

The duration of overall response for a given subject will be defined as the number of days from the day the criteria are met for CR, CRi or PR (whichever is recorded first) to the date that PD is objectively documented. The reference for PD will be the smallest measurements recorded since the treatment started. If a subject is still responding then the subject's data will be censored at the last study visit at which a tumor assessment was performed.

The distribution of the duration of overall response will be estimated using Kaplan-Meier Methodology.

8.1.3.6 ECOG Performance Status

For the ECOG performance scale, descriptive statistics will be summarized for each assessment. In addition, a mean change from baseline to each assessment will be summarized.

8.1.3.7 Reporting of Results

All subjects enrolled will be assessed for response to treatment based on the NCI-WG criteria in Section 5.3.3.1. Each subject will be assigned to one of the following categories: 1) complete remission, 2) complete remission with incomplete bone marrow recovery, 3) partial remission, 4) stable disease, 5) progressive disease, 6) early death from malignant disease, 7) early death from toxicity, 8) early death because of other cause, or 9) unknown (not assessable, insufficient data).

Subjects in response categories 5-8 will be considered as failing to respond to treatment (disease progression). Thus, an incorrect treatment schedule or drug administration will not result in exclusion from the analysis of a response.

Sub-analyses may be performed on the subset of subjects for whom major protocol deviations have not been reported (e.g., early discontinuation of treatment, major protocol violations, etc.). The reasons for excluding subjects from the analysis will be clearly reported.

8.1.4 Safety

Safety summaries will include all subjects participating in the study unless otherwise indicated. A safety analysis will be performed for all subjects in the Phase 1 portion of the study once the MTD is reached and/or RPTD is determined, after the last enrolled subject completes one cycle of drug, and prior to enrollment of subjects into the Phase 2a portion of the study. A second safety analysis will be performed for all subjects in the

Phase 1 and Phase 2a portions of the study upon completion of the study. The following will be included in these analyses:

Adverse Events

The number and percentage of subjects having treatment-emergent adverse events will be tabulated by MedDRA system organ class and preferred term.³⁸ The tabulations will also be provided with further breakdowns by NCI CTCAE toxicity grade and relationship to study drug. Serious adverse events, events leading to discontinuation of treatment, and events leading to death, will be summarized. For subjects who participate in Cycle 1 of Phase 1 of the study, all summaries will be done by dose. For the study as a whole, summaries will be provided with a breakdown as appropriate.

Platelet Counts

Platelet counts will be explored for trends with dose and time and summarized as appropriate. The baseline value (last measurement before the beginning of study drug administration) will be included in the statistical analysis and changes from baseline will be addressed.

A repeated measures model with dose level as a classification variable will be performed for values in Cycle 1 of the platelet counts for which multiple measurements will be taken. A transformation of a variable will be used if it clearly provides more nearly symmetric probability distribution and/or more nearly homogenous variances across dose levels.

The relationship between drug concentration variables and platelet counts will be explored. The dependence of observations from the same subject will be appropriately taken into account in all of the above analyses.

Other Safety Measurements

Laboratory test results, lymphocyte enumeration results, vital signs, echocardiogram results, and ECG interval measurements results will be explored for trends with dose and

time and summarized as appropriate. The baseline values (Screening values) will be included in the statistical analysis and changes from baseline will be addressed. Changes from baseline at the recommended Phase 2a dose will be analyzed with a *t*-test at each scheduled visit. Where applicable, blood chemistry and hematology determinations will be categorized according to NCI CTCAE (Version 3.0) grades, and shifts from baseline NCI CTCAE grades to maximum and final post-baseline grades for each treatment group will be assessed. Vital signs values will be evaluated for possible clinical significance using criteria developed at AbbVie. Additional analyses will be performed if useful and appropriate.

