ABT-263 induces apoptosis, rather than lysis of circulating platelets, which differs from typical chemotherapy induced thrombocytopenia related to myelosuppression. Limited human clinical data are available to understand the response to infusion of exogenous platelets in the presence of circulating drug levels. Platelet transfusion studies conducted in beagle dogs demonstrated that transfusion of one-day old platelets administered near the time of ABT-263 C_{max} , resulted in higher platelet levels than dogs not receiving supplemental platelets. Platelet concentrations remained higher after 24 hours with declining ABT-263 concentrations. This study suggests that infusion of platelets may have beneficial effects in treating acute thrombocytopenia following oral dosing with ABT-263.

From the pre-clinical models, there may be an opportunity in the monotherapy setting to increase efficacy without additional platelet toxicity in the setting of continuous dosing. In murine xenograft models of SCLC, 21 days of continuous dosing achieves superior tumor growth inhibition, greater increase in life span, and greater incidence of complete and overall response rates compared to the intermittent dosing schedules or 14 days of dosing and 7 days off drug. In a dog toxicology study, ABT-263 was delivered once daily for 28 days. At doses that achieve plasma concentrations within the targeted efficacious exposure range, circulating platelet counts recovered to baseline within 14 days of dosing and remained at baseline for the subsequent 14 days of dosing.

This observation of platelet recovery during continued ABT-263 dosing has also been observed in the Phase 1 clinical studies. Given that platelet nadirs typically occur in the first few days of dosing and circulating platelet counts recover during continued dosing, a lead-in period may help reduce the depth of platelet nadir.

ABT-263 Toxicology

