Adjustments to the dose escalation schedule may also be made based upon preliminary pharmacokinetic and safety data obtained from concurrent dose escalation studies that are being conducted with ABT-263. These decisions will be based on the judgment of the AbbVie Medical Monitor in consultation with the investigator.

Subject assessments for safety and clinical progression will continue weekly through the first 2 cycles (6 weeks). Subsequently, subject assessments for safety and clinical progression will be performed once every cycle (every 3 weeks) or more frequently, as needed.

Phase 1 -14/21 Day Dosing

ABT-263 will be administered for 14 consecutive days followed by 7 days off drug to complete a 21-day cycle. Subjects will be instructed to self-administer ABT-263 orally once daily (QD) within 30 minutes after the completion of breakfast.

Figure 3. ABT-263 Dosing Schematic – Phase 1

Additionally, a continuous dosing regimen will be evaluated and compared to the 14/21 cyclic dosing regimen.

Phase 1 – 21/21 Day Continuous Dosing

Once either the MTD is defined or dosing in the 4th dose level is completed for the 14/21 day dosing schedule, whichever occurs first, a continuous dosing schedule will be assessed. Dosing with ABT-263 under the continuous dosing schedule (21/21 day) will begin at the dose estimated to provide exposure equivalent to the highest dosing level cleared (4th dose level) or the MTD from the 14/21 day schedule. For example, if the highest dose level cleared or the MTD from the 14/21 day dosing schedule is 375 mg, the continuous starting dose (defined Cycle 1 Day 1 dose) would be $(375 \times 14)/21$ or 250 mg. A minimum of three subjects will be enrolled in each cohort. The ABT-263 dose will be

escalated using a modified CRM as described previously for the 14/21 day regimen (Figure 2).

Prior to beginning the assigned 21/21 day continuous dosing regimen, a 7-day lead-in dose titration period will be implemented. In preclinical experiments in which stepwise increases in ABT-263 doses were administered to dogs every one or two weeks, the thrombocytopenic effect of higher doses was significantly attenuated. These data combined with the clinically observed rebound in platelet counts from nadir during continued ABT-263 dosing suggest that a lead-in period may help reduce the depth of the initial platelet nadir and provide an additional margin of safety.

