- e. ECG will be performed at Screening, Day 1 and Day 14 of Cycle 1, Day 1 of each subsequent cycle and at the Final Visit for all subjects in the first 2 cohorts. ECG will be performed at Screening, Day 1 and Day 14 of Cycle 1, Day 1 and Day 14 of Cycle 3 and at the Final Visit for subjects in subsequent cohorts. Every effort should be made to obtain all ECGs approximately 4-8 hours post-dose (however, 6-8 hours post-dose is preferred), and if possible at approximately the same time of day. If pharmacokinetic data indicates the C_{max} of parent drug or a major metabolite occurs at a time different than this specified range, the timing of the ECG may be modified. Repeat ECGs will be performed whenever clinically necessary.
- f. 2D Echocardiogram with Doppler will be performed at Screening, Day 1 and Day 14 of Cycle 1, Day 1 of each subsequent cycle and at the Final Visit for all subjects in the first 2 cohorts. Echocardiogram with Doppler will be performed at Screening, Day 1 and Day 14 of Cycle 1, Day 1 and Day 14 of Cycle 3 and at the Final Visit for subjects in subsequent cohorts. Every effort should be made to obtain all echocardiograms approximately 4-8 hours post-dose (however, 6-8 hours post-dose is preferred), and if possible at approximately the same time of day. If pharmacokinetic data indicates the C_{max} of parent drug or a major metabolite occurs at a time different than this specified range, the timing of the echocardiogram may be modified. Repeat echocardiograms will be performed whenever clinically necessary.
- g. Platelet counts will be performed Cycle 1: Pre-dose on Days 1, 2, 3, 4, 5, 6, 8, 14 (in addition, at all PK time points per [Table 4](#)), Day 16 and as needed; Subsequent Cycles: Days 1, 3, 5, 8, 16 and as needed. If the investigator and the AbbVie Medical Monitor jointly agree that platelet counts through Cycle 4 have been stable, then the frequency of platelet counts in Cycle 5 and beyond may be decreased to Day 1 of each cycle and as needed. If platelet count performed on any given day is less than 50,000/mm³, additional platelet counts should be performed every day or at the discretion of the investigator.

Table 1. Schedule of Assessments – 14/21 Day Dosing (Phase 1) (Continued)

- h. Lymphocyte enumeration will be performed at Screening, Day 14 of Cycle 1, end of Cycle 4, the end of every 3rd cycle thereafter and at the Final Visit.

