Body temperature (oral or tympanic), blood pressure and pulse will be measured at Screening, Day 1 of Cycle 1, weekly through the first 2 cycles, Day 1 of each subsequent cycle (or within 72 hours prior), at the Final Visit and at the Safety Follow-up Visit. During the lead-in period (21/21 day dosing schedule), body temperature (oral), blood pressure and pulse will also be measured at Lead-in Day 1. The vital signs measurements at Screening will serve as the baseline measurements for clinical assessment. For the Extension Study, body temperature, blood pressure and pulse will be measured at Day 1, every 4 cycles (e.g., Cycle 4 Day 1, Cycle 8 Day 1, etc.), Final Visit and at the Safety Follow-up Visit.

In Phase 1, blood pressure and pulse rate will be measured approximately 30 to 60 minutes after study drug administration.

Blood pressure and pulse rate will be measured after the subject has been sitting for at least 5 minutes on days study drug is administered in the clinic.

COVID-19 Pandemic-Related Acceptable Protocol Modifications

Due to the COVID-19 pandemic, subject visits may be conducted via phone or video conference. In these situations, weight, and vital signs measurements may be performed by the subject or caregiver as needed.

Platelet Count

The platelet count measurement obtained on Cycle 1 Day 1 (pre-dose) will serve as the baseline for clinical assessment for the 14/21 day dosing schedule. The platelet count measurement obtained on Lead-in Day 1 (pre-dose) will serve as the baseline for clinical assessment for the 21/21 day dosing schedule with lead-in period.

If platelet count on any given day is less than 50,000/mm³, additional platelet counts should be performed every day or at the discretion of the investigator.

If a platelet transfusion is deemed necessary, a post-transfusion platelet count should be obtained within 10 to 60 minutes.

Platelet counts < 25,000/mm³ should be confirmed the same day by manual reading and a separate peripheral draw. Additional platelet counts will be obtained from a subject if ABT-263 is either held or interrupted per the management guidelines in Section 6.7.1 and Section 6.7.2.

All platelet count measurements obtained during Cycle 1 through Cycle 4 in the Phase 1 portion of the study will be either entered immediately on the eCRF or faxed to the Oncology Safety Management Team within 24 hours of report availability via the contact information provided in Section 6.5.

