For female subjects of childbearing potential, the local reference laboratory will perform a serum pregnancy test at Screening and a urine pregnancy test before dosing on Cycle 1 Day 1 (14/21 day dosing schedule) or Lead-in Day 1 (21/21 day dosing schedule), if it has been > 7 days since obtaining the serum pregnancy test results. The test results must be reviewed and determined to be negative prior to dosing.

Subjects considered not of childbearing potential must be documented as being surgically sterile or post-menopausal (for at least 1 year).

Survival (Phase 2a)

Survival information (i.e., the date and cause of death, post-treatment cancer therapies, etc.) will be collected at 3 month intervals after the last study visit for a period of 2 years after the subject has discontinued from the study. In Protocol Amendment #12 this information will be no longer collected.

Clinical Laboratory Tests

Phase 1

In the Phase 1 portion of the study, local laboratories will be utilized to process and provide results for the clinical laboratory tests. Subjects who move into the Extension Study from Phase 1 will continue to use local laboratories for the clinical laboratory tests. The principal investigator or sub-investigator will review, initial and date all laboratory results. The laboratory test results will be collected on the electronic Case Report Forms. The laboratory test results from the Extension Study will be collected on paper Case Report Forms.

Hematology, chemistry and urinalysis samples will be collected at Screening, Cycle 1 Day 1, Cycle 1 Days 2 and 3 (chemistry and hematology only), weekly through the first 2 cycles, Day 1 of each subsequent cycle (or within 72 hours prior), at the Final Visit and at the Safety Follow-up Visit.

For the Extension Study, hematology and chemistry will be collected at Day 1, every 4 cycles (e.g., Cycle 4 Day 1, Cycle 8 Day 1, etc.), Final Visit and at the Safety Follow-up Visit.

During the lead-in period, hematology, chemistry and urinalysis samples will also be collected on Lead-in Day 1 and Lead-in Days 2 and 3 (chemistry and hematology only).

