Changes from baseline were analyzed for each scheduled post-baseline visit and for the final visit for lymphocyte enumeration, urinalysis, blood chemistry and hematology parameters, as well as vital sign parameters.

Laboratory tests to be summarized are included in Table 1.

Table 1. Clinical Laboratory Tests

Hematology	Chemistry	Urinalysis
Hematocrit	Blood Urea Nitrogen (BUN)	Urine PH
Hemoglobin	Creatinine	Urine specific gravity
Red Blood Cell (RBC) count	Total bilirubin	Lymphocyte Enumeration
White Blood Cell (WBC) count	Serum glutamic-pyruvic transaminase (SGPT/ALT)	B-Lymphocytes total
Neutrophils	Serum glutamic-oxaloacetic transaminase (SGOT/AST)	Natural killer cells total
Bands	Alkaline phosphatase	T-Helper cells total
Lymphocytes	Sodium	T-Lymphocytes total
Monocytes	Potassium	T-Suppressor cells total
Basophils	Calcium	
Eosinophils	Inorganic phosphate	
Platelet count	Uric acid	
Reticulocyte count	Cholesterol	
Prothrombin time (PT)	Total protein	
Activated partial thromboplastin time (aPTT)	Glucose	
Mean corpuscular volume (MCV)	Triglycerides	
MPV	Albumin	
MCH	Lactate dehydrogenase (LDH)	
MCHC	Magnesium	
	Chloride	
	Bicarbonate	
	Lipase	

Mean changes from baseline at each scheduled post-baseline visit and Final Visit was summarized with the baseline mean, visit mean, change from baseline mean, standard deviation, and minimum/maximum values.

Analyses of Shift from Baseline in Clinical Laboratory Data

For shifts relative to National Cancer Institute Common Toxicity Criteria for Adverse Events (NCI CTCAE), baseline and post-baseline laboratory observations were categorized as grade 0, grade 1, grade 2, grade 3, or grade 4 according to NCI CTCAE grade version 3.0.

The baseline and final grades were defined respectively as the grade of the last measurement collected prior to the first dose of navitoclax, and as the last post-baseline

measurement collected no more than 30 days after the last dose of navitoclax. The maximum NCI toxicity grade value was the value with highest NCI toxicity grade collected after the first dose of navitoclax and within 30 days following the last dose of navitoclax. In cases where multiple values are collected on the same day, the maximum grade value was selected as the value for that day.

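### On the 14/21 schedule, late routine laboratory values (and some late platelet counts) are taken off drug, so time trends and by-dose tables mix off-drug with on-drug values

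*Protocol*

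**What the plan says.** **Dosing.** Protocol 5.1 defines the intermittent schedule: "ABT-263 will be administered for 14 consecutive days followed by 7 days off drug to complete a 21-day cycle". It adds that "a continuous dosing regimen will be evaluated and compared to the 14/21 cyclic dosing regimen". Section 3.0 lists 200 mg and 250 mg among the completed dose levels of both schedules.

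**Sampling.** In Protocol 5.3.1.1, Phase 1 hematology, chemistry and urinalysis are collected "weekly through the first 2 cycles, Day 1 of each subsequent cycle (or within 72 hours prior), at the Final Visit". Platelets on 14/21 after Cycle 1 are by default counted on Days 1, 3, 5, 8 and 16 and as needed (Table 1, footnote g). If the investigator and Medical Monitor agree that counts through Cycle 4 were stable, "then the frequency of platelet counts in Cycle 5 and beyond may be decreased to Day 1 of each cycle and as needed". In the Extension, platelets, chemistry and hematology are taken on Day 1 and then on Day 1 of every fourth cycle.

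**Analysis.** Protocol 8.1.4 says: "Platelet counts will be explored for trends with dose and time and summarized as appropriate". It plans the same exploration for other laboratory tests. It also plans a repeated measures platelet model restricted to Cycle 1. The SAP says: "Changes from baseline were analyzed for each scheduled post-baseline visit and for the final visit". It summarises laboratory data by dose and by study portion, without naming the schedule. Its adverse event tables, by contrast, are split by schedule as well as dose. Neither document has a rule for how long before the sample the last dose was taken.

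**The concern.** A Day 1 visit means different things on the two schedules. On 14/21 it closes a drug-free week; on 21/21 it falls within continuous dosing. From Cycle 3, 14/21 chemistry and hematology move from a mix of on-drug and off-drug days to off-drug days alone. If a drug effect reverses in the off week, a plot over study time can show it fading when the on-drug effect has not changed.

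A second problem sits in the SAP tables by dose. A late Day 1 row at 200 or 250 mg can average 14/21 subjects off drug with 21/21 subjects on drug. At stake are the late-cycle by-visit mean changes, the time trends, and any reading of them across schedules. For platelets, the count most likely to be missed is the one that matters: Protocol 3.0 reports that "platelet nadirs typically occur in the first few days of dosing".

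**Working it through.** There is no sample size, power or alpha figure to reproduce. The check is schedule arithmetic followed by an illustration.

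**Inputs.** 14 days on and 7 off (5.1); laboratory window up to 72 h before Day 1 (5.3.1.1 and Table 1, footnote b); platelet window 24 h before the Day 1 dose (Table 1, footnote b); platelet days from Table 1, footnote g, and Table 2, footnote g. Assumption: weekly means Days 1, 8 and 15.

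**Step 1: time since last dose on 14/21.** The Day 14 dose to the next Day 1 is 22 − 14 = 8 days = 192 h.
- Platelets at the edge of their window: 192 − 24 = 168 h.
- Laboratory tests at the edge of theirs: 192 − 72 = 120 h, or 5 days since the dose with 4 full drug-free days between.

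The protocol gives half-lives for animals only, 4.6 to 8.4 h. At 120 h the longest of these gives 120/8.4 = 14.3 half-lives. With an assumed human half-life of 24 h, 120 h is 5 half-lives and 0.5^5 = 3.1% remains; 192 h is 8 half-lives and 0.5^8 = 0.4% remains. On 21/21 the last planned dose was the day before.

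**Step 2: scheduled draws with a dose on the previous day.**

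| | 14/21 | 21/21 |
|---|---|---|
| Laboratory tests, Cycle 1 (Days 1, 2, 3, 8, 15) | 4/5 | 5/5 (Day 1 follows the lead-in) |
| Laboratory tests, Cycle 2 (Days 1, 8, 15) | 2/3 | 3/3 |
| Laboratory tests, Cycle 3 onward (Day 1) | 0/1 | 1/1 |
| Platelets, Cycle 1 | 7/9 | 7/7 |
| Platelets, later cycles, default | 3/5 (Days 3, 5, 8) | 3/3 |
| Platelets, Cycle 5 onward, if reduced | 0/1 | 1/1 |

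One exception applies to the laboratory rows: after an intra-subject escalation, safety tests are weekly for the first cycle at the new dose (5.1).

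**Step 3: what this could do to a trend.** Suppose a constant on-drug platelet fall of 60% in every cycle. (Section 5.1 gives about 60% as the mean maximal fall expected at 100 mg; holding it constant is my assumption.) Let r be the fraction recovered by the next Day 1, with 2/8 of that recovery reached by Day 16.
- Day 1 value: −60 × (1 − r).
- Mean over Days 1, 3, 5, 8, 16: −60 × [(1 − r) + 3 + (1 − r/4)]/5 = −60 × (1 − 0.25r).

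| r | Five-day mean | Day 1 only |
|---|---|---|
| 0 | −60% | −60% |
| 0.5 | −52.5% | −30% |
| 0.9 | −46.5% | −6% |
| 1 | −45% | 0% |

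Moving from the five-day schedule to Day 1 only produces apparent improvement whenever r is above zero, and none when r is zero. Section 5.6.4 reports ready reversal off drug in animals, which supports r above zero but gives no value for it.

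**The case against.** The strongest reply is that the safety conclusions do not rest on these values. DLTs and the MTD use Cycle 1. The protocol's platelet model uses Cycle 1, where seven of nine 14/21 counts are on drug. Adverse events are tabulated by schedule, and maximum grade keeps every early on-drug value. Neither 8.1.4 nor the SAP specifies a visit-matched laboratory comparison of the schedules; the intention to compare is one general sentence in 5.1. All of this stands, and it limits the point to exploratory and descriptive output.

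A reader might infer that 14/21 platelets are never seen on drug from Cycle 5. The documents do not support that. The reduction is optional, depends on agreed stability and keeps as-needed counts. Counts below 50,000/mm³ prompt further ones. Table 5 also schedules pre-dose pharmacokinetic samples on Day 14 of Cycles 6, 9, 12 and 15 and ties pre-dose samples to platelet collection, which implies on-drug counts in those cycles.

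A reader might also extend the point to vital signs, which share the visit pattern ("Day 1 of Cycle 1, weekly through the first 2 cycles, Day 1 of each subsequent cycle (or within 72 hours prior"). But 5.3.1.1 has Phase 1 blood pressure and pulse taken 30 to 60 minutes after dosing, so they cannot be called off-drug values.

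Finally, Day 1 of one cycle set against Day 1 of the next shows no artificial fading. That is correct. The artefact needs different cycle days on one time axis, as happens between the weekly laboratory visits of Cycles 1 and 2 and the Day 1 visits that follow. The plan does not exclude this, and matching Day 1 with Day 1 does not cure the pooling of schedules at one dose.

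**Conclusion.** The point holds in a limited form. From Cycle 3, scheduled 14/21 chemistry and hematology are 5 to 8 days after the last dose, apart from the escalation exception, while the same visits on 21/21 are on drug. Platelets share this in the Extension, and from Cycle 5 where the reduction is applied. Time trends and late by-visit changes are therefore confounded with off-drug sampling, and the SAP's by-dose laboratory tables can mix the two states at 200 and 250 mg.

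A reader might go further and conclude that 14/21 must look milder than 21/21, or that its toxicity must appear to fade. That does not follow. It depends on the amount of off-week recovery, which the documents do not give. Sections 3.0 and 5.1 also describe platelets recovering while dosing continues, so 21/21 values may rise too and the gap between schedules cannot be sized. The percentages above are illustrations under a constant 60% on-drug fall, not estimates. Cycle 1 DLTs, the Cycle 1 platelet model and adverse event tables are unaffected, and maximum grade is largely so.

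**What to change.** In Protocol 8.1.4 and the SAP:
- Present Phase 1 laboratory and platelet summaries by schedule as well as dose, as the adverse event tables already do.
- Flag each record as on-drug or off-drug by days since last dose, with the cut-off stated. Use actual dosing dates rather than assigned schedule, because 5.1 lets Phase 1 subjects switch schedule.
- Base time trends and any 14/21 versus 21/21 comparison on on-drug records, or on matched cycle days. Keep every on-drug count in any cycle, including Cycle 5 onward.
- Show 14/21 values from the end of the off week in a separate, labelled row.
- Leave post-dose blood pressure and pulse out of the off-drug label.

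No visit or clinical rule changes. The cost is SAP wording and one derived variable from dosing dates that subjects already record (5.5.1), for a Phase 1 portion of 29 subjects. The downside is that few on-drug 14/21 laboratory values exist after Cycle 2, so those trends will be short.
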